7.5 Exploratory (EXP) Immunogenicity Set

All subjects included in Cohort 3 who signed an additional exploratory objective informed consent form who:

- Correctly receive the vaccine (i.e., receive the vaccine to which the subject is randomized and at the scheduled time points).
- Have no major protocol deviations leading to exclusion (see [section 6.2](#)) as defined prior to unblinding / analysis.
- Are not excluded due to other reasons defined prior to unblinding or analysis (see [section 6.2](#))

7.6 Safety Set

Solicited Safety Set

All subjects in the Exposed Set with any solicited adverse event data and/or indicators of solicited adverse events (e.g., use of analgesics/antipyretics).

For the by vaccination tabulations, solicited safety sets will be defined as follows:

- Solicited safety set #1 for post-injection reactions after the first dose (SOL 1)
- Solicited safety set #2 for post-injection reactions after the second dose (SOL 2)

Unsolicited Safety Set

All subjects in the Exposed Set with unsolicited adverse event (AE) data.

In this respect, a confirmation of no AE is considered as adverse event data; hence subject is to be included.

Five Unsolicited Safety Sets will be defined:

- Unsolicited Safety Set 1: from the day of dose 1 to before dose 2 at Visit 5 (UNSOL 1-28)
- Unsolicited Safety Set 2: from the day of dose 2 at Visit 5 to the day of Visit 9 (UNSOL 29-57)
- Unsolicited Safety Set 3: From the day of dose 1 to the day of Visit 9 (UNSOL 1-57)
- Unsolicited Safety Set 4: The day of Visit 9 to study completion (UNSOL 58-394)
- Unsolicited Safety Set 5: Day 1 – Day 394 (UNSOL 1-394)

Overall Safety Set

All subjects who are in the solicited safety set and/or in the unsolicited safety set.

Subjects providing only 30 minutes post-vaccination safety data will be reported separately in a 30 minute post-vaccination safety analysis and excluded from all other safety analysis.

In case of vaccination error, subjects will be analyzed as “treated” (i.e., according to the vaccine a subject receives, rather than the vaccine to which the subject is randomized).

If a subject is unblinded during the study, he/she will be included in all the safety sets.

7.6.1 Restricted Safety Set

Not applicable

7.7 Other Analysis Set

Not applicable

7.8 Overview of Analysis Sets by PD Code

Table 7.8-1: Safety Sets

PD code	PD Description	Study Objective / Period	All Exposed Set	Overall Safety Set	Safety Set, Unsolicited AEs				Safety Set, Solicited AEs, Period (i),			
					Overall	After Dose x*	Day 1-57	Follow-Up	T6H-D7	T6H-D3	D4-D7	T30m
	Exclusion code		EXPFL	SAFFL	SSU10FL	SSU1xFL	SSU13FL	SSU14FL	SSS10FL	SSS11FL	SSS12FL	
100	Study vaccine not administered AT ALL	All Study	EXC	EXC	EXC	EXC	EXC	EXC	EXC	EXC	EXC	EXC
115	Subject did not provide any post-vaccination unsolicited safety data	All Study			EXC	EXC	EXC	EXC				
115.x	Subject did not provide any post-vaccination unsolicited safety data	Period (i)			EXC	EXC	EXC	EXC				
116	Subject did not provide any post-vaccination solicited safety data	Period (i)							EXC	EXC	EXC	EXC

EXC = excluded from this analysis set.

* After Dose x and SSU1xFL refer to After Dose 1 for SSU11FL when x=1, and After Dose 2 for SSU12FL when x=2.

Table 7.8-2: Immunogenicity Sets

PD code	PD Description	Study Objective/ Period	FAS 1	FAS x	FAS 1x	PPS 1	PPS x	PPS 1x	EXP 1	EXP x	EXP 1x
	Exclusion code		FAS1FL	FASxFL	FAS1xFL	PPS1FL	PPSxFL	PPS1xFL	EXP1FL	EXPxFL	EXP1xFL
100	Study vaccine not administered AT ALL	All Study	EXC	EXC	EXC	EXC	EXC	EXC	EXC	EXC	EXC
110.1	Serological results are not available	Visit 1 (baseline)	EXC		EXC	EXC		EXC	EXC		EXC
110.x	Serological results are not available	Visit x		EXC	EXC		EXC	EXC		EXC	EXC
112	Obvious deviation from Laboratory Manual or error in laboratory data	All Study				EXC	EXC	EXC	EXC	EXC	EXC
120	Randomization failure	All Study				EXC	EXC	EXC	EXC	EXC	EXC
120.2	Subject received another vaccine than allocated (Actual Arm different from Planned Arm)	All Study				EXC	EXC	EXC	EXC	EXC	EXC
130	Randomization code was broken	All Study				EXC	EXC	EXC	EXC	EXC	EXC
140	Vaccination not according to protocol					EXC	EXC	EXC	EXC	EXC	EXC
140.4	Incomplete vaccination series (only 1 st dose administered)	All Study					EXC*	EXC		EXC*	EXC
150	Administration of forbidden vaccine										

PD code	PD Description	Study Objective/ Period	FAS 1	FAS x	FAS 1x	PPS 1	PPS x	PPS 1x	EXP 1	EXP x	EXP 1x
	Exclusion code		FAS1FL	FASxFL	FAS1xFL	PPS1FL	PPSxFL	PPS1xFL	EXP1FL	EXPxFL	EXP1xFL
200	Subject did not meet entry criteria	All Study				EXC	EXC	EXC	EXC	EXC	EXC
220	Subject had contraindication for a subsequent study vaccination but was vaccinated	Visit 5				EXC	EXC	EXC	EXC	EXC	EXC
230	Administration of forbidden medication					EXC	EXC	EXC	EXC	EXC	EXC
240	Underlying medical condition forbidden by the protocol					EXC	EXC	EXC	EXC	EXC	EXC
250	Concomitant infection related to the vaccine which may influence immune response					EXC	EXC	EXC	EXC	EXC	EXC
260.1	Did not comply with study vaccination schedule	Dose 1				EXC	EXC	EXC	EXC	EXC	EXC
260.x	Did not comply with study vaccination schedule	Dose 2					EXC	EXC		EXC	EXC
270	Did not comply with blood draw schedule					EXC	EXC	EXC	EXC	EXC	EXC

PD code	PD Description	Study Objective/ Period	FAS 1	FAS x	FAS 1x	PPS 1	PPS x	PPS 1x	EXP 1	EXP x	EXP 1x
	Exclusion code		FAS1FL	FASxFL	FAS1xFL	PPS1FL	PPSxFL	PPS1xFL	EXP1FL	EXPxFL	EXP1xFL
280	Subject who developed withdrawal criteria but was not withdrawn	Visit x					EXC	EXC		EXC	EXC
290	Early withdrawal	Visit x		EXC	EXC		EXC	EXC		EXC	EXC

*except from PPS 5 as deviation would occur after blood draw for day 29 assessment.

FAS = Full Analysis Set; PPS=Per Protocol Set; EXP=Exploratory Immunogenicity Set, EXC = excluded from this analysis set.

FAS 1, PPS 1, and EXP 1 refer to any immunogenicity analyses including values for baseline.

FAS x, PPS x, and EXP x refer to any immunogenicity analyses including values for visit x (i.e. visits after V1 with immunogenicity evaluation).

FAS 1x, PPS 1x, and EXP 1x refer to any immunogenicity analyses including values for baseline and visit x.

Code 999 is not a protocol deviation but it will lead to exclusion.

8. GENERAL ISSUES FOR STATISTICAL ANALYSES

8.1 Adjustment for Covariates

The log-transformed antibody titers at the time points where a blood draw for immunogenicity is collected will be analyzed using an Analysis of Covariance (ANCOVA) model which includes the vaccine-group effect (see [section 11.2](#)) and an effect defined by the log-transformed pre-vaccination antibody titer as an independent variable. Summary tables will show adjusted geometric mean titers (GMTs) for each vaccine group.

Binary data tables will show unadjusted percentages.

8.2 Handling of Dropouts, Missing Data

8.2.1 Safety Data

For unsolicited adverse events, the entire study period will be divided into the following intervals: “day 1 – day 28, day 29 – day 57, day 58 – day 394”.

For solicited adverse events, the solicited study period “30 min - day 7” will be divided into: “30 min, 6h - day 3, day 4 - day 7, and 6h - day 7”.

No imputation methods will be used to address missing values.

8.2.2 Immunogenicity Data

Missing immunogenicity values are considered missing completely at random (MCAR) and therefore will not contain information that impact the result of the analysis (i.e., not informative). Imputation methods will therefore not be used.

Population of analyses:

PPS will be considered the principal analysis set. The primary immunogenicity analyses will be conducted on the PPS and will be repeated using the FAS as a measure of robustness. All other primary and secondary immunogenicity analyses will be based on the PPS.

The exploratory immunogenicity analyses will be based on the EXP.

8.2.3 Efficacy Data

Not applicable.

8.3 Multicenter Studies

Not applicable as this is a single center study.

8.4 Multiple Comparisons and Multiplicity

Statistical tests will only be used for descriptive purposes therefore no multiplicity adjustment will be done.

8.5 Immunogenicity/Safety/Other Subsets

Not applicable.

8.6 Subgroups

Not applicable.

8.7 Derived and Computed Variables

Demographics

Age will be calculated in years using the following formula:

$$(\text{Date of Visit 1} - \text{Date of Birth} + 1) / 365.25$$

Body Mass Index (kg/m²) will be calculated using the following formula:

$$\text{Weight (kg)} / \text{Height}^2 (\text{m}^2)$$

Immunogenicity

Values below the limit of quantification (LLQ = 1:100, recorded as “< LLQ”) will be set to half that limit (i.e., LLQ/2 = 1:50).

Geometric Mean Titer

The GMT will be calculated using the following formula:

$$10^{\left\{ \frac{\sum_{i=1}^n \log_{10}(t_i)}{n} \right\}}$$

where t_1, t_2, \dots, t_n are n observed immunogenicity titers/concentrations.

Ratio greater or equal to a given threshold is defined for non-missing values as:

= 1, if the concentration relative to pre-vaccination is superior or equal to the given fold-rise threshold

= 0, otherwise

Value of 4 fold-rise will be used.

Duration in the Study

Duration in the study is defined in days as:

Last visit date (visit x)^a – Enrollment date (visit 1) + 1

^aor premature discontinuation date (in case of withdrawal from the study)

The duration is missing if one of the dates is missing or incomplete.

Duration in the study after vaccination 1 is defined in days as:

Date of vaccination 2 (visit 5) – Date of vaccination 1 (visit 2)

Duration in the study after vaccination 2 is defined in days as:

Date of vaccination 2 follow-up (visit 9) – Date of vaccination 2 (visit 5)

Solicited Adverse Events

For details see [section 13.2](#).

Unsolicited Adverse Events

All adverse events will be characterized according to the date of occurrence related to the vaccination phase as follows:

- **Emergence before vaccination phase:** start date before the first date of injection of study vaccine.
- **Emergence during vaccination phase:** start date on or after the first date of injection of study vaccine or, adverse event increase in severity including to “serious” adverse event.

If start date is equal to the first date of injection then “timing” variable (“On injection day, before injection”/“On injection day, after injection”) will be used to define whether the adverse event occur before or after the injection.

If there are several vaccinations, the adverse event will be associated with the most recent vaccination.

If an adverse event start date is missing or unknown, the adverse event will be considered as emergent.

When start and/or end dates of an adverse event are only partially known, adverse events will be categorized as emergent before, during, or after vaccination phase using the following rules:

- If the partial end date is before ($<$) the first study vaccination (i.e., year or year & month is/are before the first study vaccination year or year & month) then the adverse event is emergent before vaccination phase.
- If the partial start date is equal or after (\geq) the first study vaccination (i.e., year or year & month is/are after or the same as the first study injection year or year & month) then the adverse event is emergent during vaccination phase.

The **maximum event severity** is the greatest severity associated with a preferred term (PT) for a reported adverse event according to the following order: Mild $<$ Moderate $<$ Severe. Unknown/ Missing severity is considered as severe (except for the definition of emergence).

Multiple AEs with the same PT for the same subject are counted only once.

Vaccination-related Adverse Events are those for which the relationship has been evaluated by the investigator, and recorded either as possibly related, probably related or unknown/ missing.

Safety Laboratory Data

All laboratory measurements summarized in the CSR are those defined in the study protocol. All laboratory tests including retests and reasons for retests will be presented in the data listings for each subject. In case of multiple measurements of a laboratory parameter for a subject:

1. Before the study vaccination, only the latest measurement, with closest date before ($<$) the first study vaccination date, will be retained for analysis.
2. After the study vaccination, only the first measurement, with soonest date after ($>$) the last study vaccination date, will be retained for analysis.

Reference ranges used to categorize the results as “low” (values below the lower limit of the reference range), “normal” (values within the reference range) or “high” (values above the upper value of the reference range) will be those provided by Quintiles Laboratories, which performed the tests and provided the laboratory reports.

Pre-study, Concomitant and Post-Vaccination Medications

A **previous medication** is a medication used only before the first study vaccination (i.e. medication end date < first study vaccination date).

All other medications are **concomitant**.

When start and/or end dates of a medication intake are missing, the medication is considered as concomitant with the study vaccination schedule.

If the first study vaccination date is missing then the medication is considered as concomitant with the study vaccination schedule, provided that the study vaccine was administered to the subject.

For further details please refer to the technical and program specifications document stored in ^{PPD} within the SAS Drug Development (SDD) server.

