3. STUDY DESIGN

This is a Phase 1, randomized, observer blind, placebo-controlled, dosage-escalation, single center study, enrolling healthy adults. In total, approximately 288 healthy non-pregnant female and male adults (18 to 45 years of age) will be enrolled in the study in the ratio of 3:1. There is a higher ratio of female to male subjects because the RSV F subunit vaccine is ultimately intended for use in pregnant women. Men are still being included in this study because the vaccine may also be tested in the future in elderly subjects.

Approximately 288 healthy subjects will be enrolled (1:1:1) in a stepwise dosage-escalation manner in to one of three cohorts (cohort 1: low dosage of RSV F subunit vaccine [45 µg], cohort 2: middle dosage of RSV F subunit vaccine [90 µg], and cohort 3: high dosage of RSV F subunit vaccine [135 µg]). Cohort 1 will be enrolled first, followed by cohort 2, and finally cohort 3. Within each cohort subjects will be randomly allocated (1:1:1:1) to receive vaccine with no adjuvant, vaccine with aluminum hydroxide, vaccine with MF59, or saline placebo, as outlined in [Table 4-1](#). All subjects will receive two doses of a 0.5 mL intramuscular injection of the vaccine, with adjuvant (aluminum hydroxide [1 mg] or MF59 [0.25 mL; 9.75 mg squalene and surfactants]), the vaccine without adjuvant, or saline placebo. There will be approximately 24 subjects in each active treatment group and 24 placebo subjects per cohort) ([Table 4-1](#)).

The schedule of time and events, including whether a visit is a telephone call or a clinic visit is displayed in [Table 3-1](#).

Table 3-1: Times and Events Table

Study Period	Screen	Vaccine Dose #1 & Safety Follow-up				Vaccine Dose #2 & Safety Follow-up					Post-vaccination Follow-up				
		Clinic Visit	Clinic Visit	Reminder Call	Clinic Visit	Phone Call	Clinic Visit	Reminder Call	Clinic Visit	Phone Call	Clinic Visit	Clinic Visit	Clinic Visit	Clinic Visit	Clinic Visit
Study Day	-28 to -3	1	3, 5	8	15, 22	29	31, 33	36	43, 50	57	85	113	181	209	271, 366, 394
Days post 1 st dose		0	2, 4	7	14, 21	28	30, 32	35	42, 49	56					
Days post 2 nd dose						0	2, 4	7	14, 21	28	56				
Study Visit Window (min-max) in Days (d)	n/a	n/a	-1/+1	-1/+4 d	-1/+1	+14 d	-1/+1	-3/+3 d	-1/+1	-7/+7 d	-7/+7 d	-7/+7 d	-7/+7 d	-14/+14 d	-7/+7 d
Visit Number	Screening	1		2	3, 4	5		6	7, 8	9	10	11	12	13	14, 15, 16
Informed Consent	X														
Medical History	X														
Physical Exam ^a	X	X ^b		X		X ^b		X		X	X	X	X	X	

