Assess for AESIs ^p		X		X		X		X		X	X	X	X	X	X
Prior/Concomitant Medications/vaccines ^q	X	X		X		X		X		X	X	X	X	X	
Study Termination ^r															X

- Physical examination must be performed by a qualified health professional in accordance with local regulations and licensing requirements designated within the Site Responsibility Delegation Log. See protocol [section 6.2](#) for components of physical examination by visit.
- Procedure to be performed prior to vaccination.
- Safety laboratory assays that will be included are listed in protocol [section 3.5.3](#).
- Urinalysis testing will include at a minimum protein, glucose, and presence of red blood cells.

- e. Maximal blood draw refers to volume drawn for each type of assay at each specified visit. See protocol [section 3.5.1](#) for greater detail regarding blood sampling volumes.
- f. The first 10 subjects enrolled in each treatment group of Cohort 3 who agree to the additional blood draws will need to sign an additional consent prior to the blood draw for the secondary exploratory objective.
- g. Subjects will receive two doses of vaccine or placebo according to the study randomization scheme.
- h. A 30 minute post-injection local and systemic adverse event and body temperature measurement will be performed by the subject under site staff supervision at the clinic during Visit 1 and Visit 5.
- i. Beginning 6 hours following study vaccine administration at Visit 1 and Visit 5, and daily thereafter through 7 days after each vaccination, solicited local and systemic adverse events including other reactions (i.e. body temperature measurements and use of analgesics/antipyretics) will be reported daily by the subject on a diary card.
- j. Subjects will receive training on the diary card at Visit 1 and Visit 5.
- k. The diary card will be dispensed at Visit 1 and Visit 5, and subjects will be reminded that diary cards must be returned at the next clinic visit (Visit 2 or Visit 6).
- l. Site staff will contact subjects by phone 2 and 4 days after each vaccination to remind them to complete their diary cards each day, and to bring the diary cards to their next clinic visit.
- m. Review of safety data captured on diary cards will be completed at Visit 2 and Visit 6. Diary cards will be collected and stored with subject files.

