9. STUDY SUBJECTS

9.1 Disposition of Subjects and Withdrawals

All subjects who provide informed consent will be accounted for in this study. The frequencies and percentages of subjects in each analysis set, study withdrawals, subgroups, and major protocol deviations will also be presented.

The time the subjects are under observation will be summarized by vaccine and overall using summary statistics (mean, SD, minimum, median, maximum).

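### SAP section 8.7 labels the vaccination 1 date with the wrong visit and gives neither per-vaccination duration an end date for subjects who leave early

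*SAP*

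**What the plan says.** The point concerns the latest of the three SAP versions in the file. Only that version contains the two per-vaccination durations.

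- Section 8.7, duration after vaccination 1: "Date of vaccination 2 (visit 5) – Date of vaccination 1 (visit 2").
- Section 8.7, duration after vaccination 2: "Date of vaccination 2 follow-up (visit 9) – Date of vaccination 2 (visit 5").
- Section 8.7, overall duration: it runs from Visit 1 to the last visit, plus one day. A footnote lets the discontinuation date stand in for the last visit when a subject withdraws. The value is set to missing if either date is missing or incomplete.
- Section 3, Table 3-1, footnote i, on when vaccine is given: "Beginning 6 hours following study vaccine administration at Visit 1 and Visit 5".
- Section 3, Table 3-1, footnote m, on what Visit 2 is for: "Review of safety data captured on diary cards will be completed at Visit 2 and Visit 6".
- Section 9.1, on reporting: "The time the subjects are under observation will be summarized by vaccine and overall".
- Section 7.6: the first-dose unsolicited safety period (UNSOL 1-28) starts on the day of dose 1 and stops before dose 2 at Visit 5.
- Section 7.8, Table 7.8-2: code 140.4 covers subjects who received only the first dose.

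**The concern.** There are two faults in the same pair of formulas.

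The first is the start point. No vaccine is scheduled at Visit 2, so a vaccination 1 date cannot come from that visit. The other visit labels in this block (Visit 1 for enrollment, Visit 5 for vaccination 2, Visit 9 for follow-up) agree with the schedule; this one does not. A programmer who takes the date from the labelled visit starts the clock about a week late.

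The second is the end point. The vaccination 1 formula needs a dose 2 date and the vaccination 2 formula needs a Visit 9 date. Neither has the fallback given to the overall duration a few lines above. The SAP expects incomplete series, and section 6.2 mentions premature withdrawal for adverse events or withdrawn consent. These subjects would have no per-dose follow-up time, although in a first-in-human safety study they are the ones whose follow-up a reader is most likely to ask about.

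**Working it through.** **Inputs, all from SAP section 3, Table 3-1**

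- Study days: Visit 1 = Day 1, Visit 2 = Day 8, Visit 5 = Day 29, Visit 9 = Day 57.
- Windows: Visit 2 is −1/+4 days, so Day 7 to 12. Visit 5 is +14 days, so Day 29 to 43.
- Time since dose 1: "Days post 1 st dose 0 2, 4 7 14, 21 28". This is 0 at Visit 1, 7 at Visit 2 and 28 at Visit 5.

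**Step 1: reproduce the plan's own interval.** Visit 5 − Visit 1 = 29 − 1 = 28 days, which agrees with the table row.

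**Step 2: apply the formula with the labelled visit.** Visit 5 − Visit 2 = 29 − 8 = 21 days. The shortfall is 28 − 21 = 7 days, and 7/28 = 25%.

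**Step 3: apply the windows.**

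| Start date used | Nominal | Shortest | Longest |
|---|---|---|---|
| Visit 1 (injection) | 29 − 1 = 28 | 29 − 1 = 28 | 43 − 1 = 42 |
| Visit 2 (as labelled) | 29 − 8 = 21 | 29 − 12 = 17 | 43 − 7 = 36 |

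For an individual subject the loss is the Visit 2 day minus Day 1: from 7 − 1 = 6 to 12 − 1 = 11 days.

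**Step 4: subjects who do not complete.** This needs no arithmetic.

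- Dose 1 only: there is no vaccination 2 date, so duration after vaccination 1 has no value from either start date. This includes subjects who miss dose 2 but stay in follow-up.
- Dose 2 given, but left before Visit 9: there is no Visit 9 date, so duration after vaccination 2 has no value.

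**Step 5: the one-day convention.** The overall duration adds one day and the per-vaccination formulas do not. With one day added to both, an on-schedule subject would have (29 − 1 + 1) + (57 − 29 + 1) = 29 + 29 = 58 days, against 57 calendar days in UNSOL 1-57, because the dose 2 day falls in both intervals. Without the extra day, the vaccination 1 duration is 28 days, which matches UNSOL 1-28.

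**The case against.** The strongest reply is that the visit label is a slip in brackets. The operand is named as the date of vaccination 1, and a programmer who uses the injection date gets the correct 28 days. That stands: the 21-day figure is conditional, and a reader should not infer that the SAP certainly loses a week. What remains is that the line supports two answers.

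A reader might also infer that the per-dose values feed the observation-time summary in section 9.1. The document does not say so. The same sentence stands in the two earlier SAP versions in the file, where section 8.7 had no per-vaccination durations, so it fits the overall duration equally well. Likewise, no passage says that the vaccination 1 duration was built to describe UNSOL 1-28; the two merely run in parallel.

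Nor would early leavers disappear from the report. They remain in the overall duration through the discontinuation date, in the withdrawal counts of section 9.1 and in the vaccination counts of section 13.1.

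Finally, section 8.7 refers further derivation detail to a technical specification that is not in the document and may settle some of this. None of these replies supplies an end date for incomplete series in the SAP itself.

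**Conclusion.** The point holds as a faulty derivation rule with limited consequences.

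- **Label:** the visit named for vaccination 1 is wrong. The cost is 7 days nominally (25% of 28; 6 to 11 days within windows), provided the visit date is used rather than the injection date.
- **End date:** under either reading, both per-vaccination durations are undefined for subjects who do not reach the end event, so any per-dose summary would describe completers only. The SAP gives no expected number of such subjects, so the share lost is not estimated here.
- **Reach:** only descriptive observation time is affected. The overall duration has the correct start and a fallback. No immunogenicity endpoint, adverse event percentage or analysis-set rule is stated to use the per-vaccination durations, so the document does not support reading this as a threat to the primary or safety results.

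**What to change.** In SAP section 8.7:

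1. Change the visit label for vaccination 1 from Visit 2 to Visit 1.
2. End the duration after vaccination 1 at the date of vaccination 2. If dose 2 is not given, end it at premature discontinuation or, for subjects who stay in follow-up, at the Visit 9 or last-contact date.
3. End the duration after vaccination 2 at the earlier of Visit 9 and premature discontinuation.
4. Do not add one day to both formulas. Keep the vaccination 1 duration at 28 days for an on-schedule subject, so that it matches UNSOL 1-28, and state the day-count convention once for both.
5. Say in section 9.1 whether the per-vaccination durations are to be tabulated.

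The cost is a few lines of SAP text and a small change to the derivation program. It uses dates the trial already collects and needs no change to visits or data capture.

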Safety Laboratory Blood draw [max: 10 mL whole blood] ^c	X	X ^b		X		X ^b		X		X					
Urinalysis ^d	X	X ^b		X		X ^b		X		X					
Pregnancy Test	X	X ^b				X ^b									
Exclusion/Inclusion Criteria	X														
Randomization		X ^b													
Serology Blood draw [max: 15 mL whole blood] ^e		X ^b				X ^b				X			X		

Study Period	Screen	Vaccine Dose #1 & Safety Follow-up				Vaccine Dose #2 & Safety Follow-up					Post-vaccination Follow-up				
Type of Visit	Clinic Visit	Clinic Visit	Reminder Call	Clinic Visit	Phone Call	Clinic Visit	Reminder Call	Clinic Visit	Phone Call	Clinic Visit	Clinic Visit	Clinic Visit	Clinic Visit	Clinic Visit	Phone Call
Study Day	-28 to -3	1	3, 5	8	15, 22	29	31, 33	36	43, 50	57	85	113	181	209	271, 366, 394
Days post 1 st dose		0	2, 4	7	14, 21	28	30, 32	35	42, 49	56					
Days post 2 nd dose						0	2, 4	7	14, 21	28	56				
Study Visit Window (min-max) in Days (d)	n/a	n/a	-1/+1	-1/+4 d	-1/+1	+14 d	-1/+1	-3/+3 d	-1/+1	-7/+7 d	-7/+7 d	-7/+7 d	-7/+7 d	-14/+14 d	-7/+7 d
Visit Number	Screening	1		2	3, 4	5		6	7, 8	9	10	11	12	13	14, 15, 16
2 ^o Exploratory Obj. Blood Draw [max: 50 mL whole blood] ^f		X ^b		X		X ^b							X		
Study Vaccine Administered ^g		V				V									
30 Minutes Post Injection Assessment (Local/ Systemic AEs, Body Temperature) ^h		X				X									
Local/Systemic AEs, Body Temperature, Other Indicators of Reactogenicity ⁱ		X				X									
Diary Card Training ^j		X				X									
Diary Card Dispensed ^k		X				X									
Diary Card Reminder Call ^l			X				X								

Study Period	Screen	Vaccine Dose #1 & Safety Follow-up				Vaccine Dose #2 & Safety Follow-up					Post-vaccination Follow-up				
Type of Visit	Clinic Visit	Clinic Visit	Reminder Call	Clinic Visit	Phone Call	Clinic Visit	Reminder Call	Clinic Visit	Phone Call	Clinic Visit	Clinic Visit	Clinic Visit	Clinic Visit	Clinic Visit	Phone Call
Study Day	-28 to -3	1	3, 5	8	15, 22	29	31, 33	36	43, 50	57	85	113	181	209	271, 366, 394
Days post 1 st dose		0	2, 4	7	14, 21	28	30, 32	35	42, 49	56					
Days post 2 nd dose						0	2, 4	7	14, 21	28	56				
Study Visit Window (min-max) in Days (d)	n/a	n/a	-1/+1	-1/+4 d	-1/+1	+14 d	-1/+1	-3/+3 d	-1/+1	-7/+7 d	-7/+7 d	-7/+7 d	-7/+7 d	-14/+14 d	-7/+7 d
Visit Number	Screening	1		2	3, 4	5		6	7, 8	9	10	11	12	13	14, 15, 16
Diary Card Reviewed and Collected ^m				X				X							
Telephone Contact for Review of Safety Data ⁿ					X				X						
Assess all AEs, including SAEs and NOCDs Leading or not to Study Withdrawal ^o		X		X		X		X		X	X	X	X	X	X

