13.5 Clinical Safety Laboratory Investigations

Clinical safety laboratory values, and change-from-baseline values (study day 8, 29, 36 and 57 vs. day 1), will be summarized (mean, standard deviation, median, minimum and maximum) at each time-point of assessment, by vaccine group, for subjects in the Overall Safety Set with available laboratory data.

The frequencies of subjects with clinical laboratory values below, within, or above normal ranges will be tabulated for each clinical laboratory variable by vaccine-group and time-point of assessment (3 x 3 shift tables).

The percentages of subjects that show a 'range change abnormal high' (RCAH) or a 'range change abnormal low' (RCAL) are to be tabulated for each clinical laboratory variable by vaccine-group and time point of assessment. A RCAH is a laboratory value that is low or normal at baseline but high post-baseline. A RCAL is a laboratory value that is normal or high at baseline but low post-baseline.

Laboratory values will also be classified and tabulated according to CBER toxicity criteria (CBER 2007b, see section 19 for reference).

Laboratory values that are outside the normal range will also be flagged in the data listings, along with corresponding normal ranges and assessment of clinical significance.

For subjects presenting at least one clinically significant value, an additional listing will be provided of all laboratory results by vaccine group, by subject, and by relevant parameter. Clinical significance assessed by the investigator will be presented.

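### The laboratory selection rule in SAP Section 8.7 rejects the Day 1 baseline that Section 13.5 requires and, read literally, up to three of the four post-baseline visits

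*SAP*

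**What the plan says.** Section 8.7 of the SAP (Safety Laboratory Data) first sends all laboratory tests, with retests and their reasons, to the data listings. It then sets a selection rule that opens "In case of multiple measurements of a laboratory parameter for a subject". There are two parts:

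- Rule 1: "Before the study vaccination, only the latest measurement, with closest date before" (<) the first study vaccination date, is kept.
- Rule 2: "After the study vaccination, only the first measurement, with soonest date after" (>) "the last study vaccination date, will be retained for analysis".

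Section 13.5 states what the tables must contain: laboratory values and "change-from-baseline values (study day 8, 29, 36 and 57 vs. day 1), will be summarized". Shift tables and the percentages with a range change to abnormal high or low are also required at each time point.

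Table 3-1 in Section 3 places safety laboratory draws at screening (Day -28 to -3) and on Days 1, 8, 29, 36 and 57. The Day 1 and Day 29 draws carry footnote b: "Procedure to be performed prior to vaccination". The two preceding SAP versions in the same file contain the same rule and the same Section 13.5 requirement.

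**The concern.** The selection rule suits a design with one dose and one sample on either side of it. This study has two doses and six scheduled draws. The trigger has no limit to a visit or time point, so on its wording every subject who follows the schedule meets it. Rule 1 uses a strict date comparison, although the intended baseline sample is taken on the vaccination date. Rule 2 counts from the last vaccination, although two of the required post-baseline draws come before or on that date.

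At stake are the change-from-baseline summaries, shift tables, range-change percentages and toxicity grading in a first-in-human study with safety as a primary objective. A programmer cannot follow both sections. One who departs from Section 8.7 has to choose the baseline and the visit selection without written authority.

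**Working it through.** No sample-size or power figure is involved. The check applies the two date tests to the scheduled draws.

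**Inputs**
- Draws (Table 3-1): screening, Days 1, 8, 29, 36, 57.
- First vaccination: Day 1. Last vaccination for a two-dose subject: Day 29. Nominal days are used.
- The Day 1 and Day 29 draws are dated the same as the injection (footnote b).
- Values needed by Section 13.5: Days 1, 8, 29, 36, 57.

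**Literal rule, two-dose subject**

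| Draw | Before Day 1? | After Day 29? | Kept |
|---|---|---|---|
| Screening | yes, latest | no | yes, as baseline |
| Day 1 | no, same date | no | no |
| Day 8 | no | no | no |
| Day 29 | no | no, same date | no |
| Day 36 | no | yes, first | yes |
| Day 57 | no | yes, not first | no |

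Of the five values needed, one is kept (Day 36). Of the four post-baseline visits, three are lost: 3/4 = 75%.

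**Other readings**

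| Reading | Kept | Needed values lost | Post-baseline visits lost |
|---|---|---|---|
| Literal | screening, 36 | 1, 8, 29, 57 | 3 of 4 |
| Last vaccination means most recent dose | screening, 8, 36 | 1, 29, 57 | 2 of 4 |
| One value per visit, dates as written | screening, 36, 57 | 1, 8, 29 | 2 of 4 |
| Both leniencies together | screening, 8, 29, 36, 57 | 1 | 0 of 4 |

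For a subject who received only the first dose, the literal rule keeps screening and Day 8 and loses Days 1, 29, 36 and 57.

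The post-baseline loss therefore depends on the reading, from 0 to 3 of 4 visits. Day 1 is lost in every row, because a sample dated on the vaccination day is not dated before it. Rule 1 also pulls against itself: the latest measurement before vaccination is the pre-injection Day 1 draw, but the date test removes it. In the same section, the adverse event rules deal with same-day events through a variable recording whether onset came before or after the injection. The laboratory rule has no such provision.

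**The case against.** The strongest reply is that the rule is a contingency for retests. It follows directly on a sentence about retests, and it is conditional in form, which is odd wording for something true of every subject by schedule. Section 13.5 is the more specific text and names both the baseline and the time points. Section 8.7 also refers to a technical and program specifications document, not shown here, which may define visit selection and repeats.

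Much of this stands. A retest purpose is likely, and a team that saw mostly empty tables would probably question the literal rule. But the limit to retests is not written. If the rule is held to be silent when no test is repeated, Day 1 can stand as baseline on the strength of Section 13.5 alone. Once rule 1 is applied, though, no sample dated Day 1, and no repeat of it that day, can pass the date test. A programming specification should carry out the SAP, not correct it.

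A reader might go further and infer that all laboratory data after dose 1 are lost, that a 75% loss is certain, or that safety signals would go unseen. The document does not support this. Day 36 follows dose 1 and survives for two-dose subjects. The 75% belongs to the literal reading only. Every result is listed, out-of-range values are flagged with normal ranges and an assessment of clinical significance, and subjects with a clinically significant value get an additional listing. Section 15 separately provides for a data monitoring committee to review safety data during the study.

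**Conclusion.** Section 8.7 is wrong as written and conflicts with Section 13.5. The baseline conflict is firm: wherever rule 1 is applied, the Day 1 sample is excluded and the screening value from Day -28 to -3 takes its place. The post-baseline conflict depends on the reading. At worst, a two-dose subject loses Days 8, 29 and 57 (3 of 4 visits) from the summary tables; on the most lenient reading tried, none is lost. The loss concerns tabulated analyses only.

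This rests on two assumptions: that the Day 1 and Day 29 samples are dated the same as the injection, as the schedule implies, and that no unseen specification overrides the SAP text.

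**What to change.** Replace the two rules in Section 8.7 with two sentences:

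1. Baseline is the last value taken before the first injection, including the pre-injection Day 1 sample; the screening value is used only if Day 1 is missing.
2. The multiple-measurement rule applies only to repeats within a scheduled visit, so that one value is kept at each of Days 8, 29, 36 and 57. The present preference for the first measurement can serve as the tie-break within a visit.

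All five values that Section 13.5 needs are then kept (5 of 5, against 1 of 5 under the literal rule). The cost is two sentences and the matching derivation code, with no new data collection. A table of the worst post-baseline toxicity grade, counting retests, would be an optional addition and is not part of this correction.
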